4.2 Subject Exclusion Criteria

Subjects will be excluded for any of the following conditions/reasons:

1. Women who are pregnant, lactating, breast feeding or have a positive serum pregnancy test at enrollment or positive urine pregnancy test on the morning of each study session.
2. Smokers/tobacco users (current use or use over the previous 2 months of nicotine-containing substances (e.g., cigarettes, cigars, chewing tobacco, snuff, gum, patch or electronic cigarettes).
3. Participation in any ongoing investigational drug trial/study or clinical drug trial/study.
4. History as either reported by the subject or evident to the Medically Accountable Investigator (MAI) of infectious disease or skin infection or of chronic skin disease (e.g., psoriasis, atopic dermatitis).
5. History of diabetes.
6. History of significant dermatologic cancers (e.g., melanoma, squamous cell carcinoma), except basal cell carcinomas that were superficial and did not involve the investigative site.
7. Body Mass Index (BMI) ≥ 30 kg/m².
8. History of chronic obstructive pulmonary disease or cor pulmonale, or substantially decreased respiratory reserve, hypoxia, hypercapnia or pre-existing respiratory depression.
9. Active positive Hepatitis B, C and/or HIV serologies (see *Appendix B*).

-
10. Positive urine drug screening test.
 11. Use of chronic prescription medications during the period 0 to 30 days; or over-the counter medications (e.g. antihistamines, topical corticosteroids) and short term (<30 days) prescription medications during the period 0-3 days before a study session (vitamin, herbal supplements and birth control medications not included).
 12. Currently taking daily anticoagulants (warfarin, heparin, rivaroxaban, dabigatran, etc...) within the past month prior to entry into the study.
 13. Have Crohn's disease.
 14. History of blood dyscrasia.
 15. Donation or loss of greater than one pint of blood within 60 days of entry to the study.
 16. Any prior adverse reaction or hypersensitivity to metronidazole, parabens, other inactive ingredients in the gels or cream or to medical tape products.
 17. Received an experimental agent (vaccine, drug, biologic, device, blood product or medication) within 1 month before enrollment in this study or expects to receive an experimental agent during the study.
 18. Consumption (food or drink) of alcohol within 48 hours prior to dose administration.
 19. Any condition that would, in the opinion of the Medically Accountable Investigator (MAI), place the subject at an unacceptable risk of injury or render the subject unable to meet the requirements of the protocol.
 20. Subject has an obvious difference in skin color between arms or the presence of a skin condition, excessive hair at the application site (upper arms), sunburn, raised moles and scars, open sores at application site (upper arms), scar tissue, tattoo, or coloration that would interfere with placement of metronidazole products, skin assessment, or reactions to metronidazole.

5 PHARMACOKINETICS AND STATISTICAL CONSIDERATIONS

5.1 Analyses

Metronidazole concentrations will be measured in serum samples collected from each subject. Blood samples (approximately 5 mL (1 tsp)) will be collected during each study session within -60 min prior to gel or cream application and then at 1 h, 2 h, 3 h, 4 h, 5 h, 6 h, 7 h, 8 h, 9 h, 10 h, 23 h, 24 h and 25 h post-application. Non compartmental analyses (NCA) will be conducted to estimate the PK parameters such as: maximum serum concentration (C_{max}) and AUC of the serum concentration–time determined by the linear trapezoidal method. All NCA analyses will be conducted using Phoenix® WinNonlin® 6.4 (Pharsight, a Certara Company, CA).

5.2 Final Analysis Plan

The objective of this study is to determine PK parameters (C_{max} , AUC) of metronidazole in healthy adults after using metronidazole 0.75% gels or cream.

Student's t-test or Analysis of variance (ANOVA) followed by post-hoc Bonferroni test will be used, where appropriate, for comparing the differences in the means of the PK parameters and significant differences will be declared at $p < 0.05$.

If metronidazole PK concentrations are found to be non-normally distributed, then we will examine Box-Cox transformations (e.g., log, square-root, etc.) that can achieve normality. If no transformation can achieve normality, then will use permutation tests to compute empirical p -values, and will use the bootstrap to compute standard errors and confidence intervals that account for within-person correlation.

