Description of Study Design:	
The study will be an open-label, crossover study over 10 weeks (n=12 healthy subjects) with one week washout period between studies.
 
The study contain six procedure days:
 
• Procedure Day 1: RLD topical gel containing 0.75% metronidazole to be applied for 25 h. Blood samples obtained on Procedure Day 1 and 2.• Procedure Day 3: Generic topical gel containing 0.75% metronidazole to be applied for 25 h. Blood samples

obtained on **Procedure Day 3 and 4.**

- **Procedure Day 5:** Generic topical cream containing 0.75% metronidazole to be applied for 25 h. Blood samples obtained on **Procedure Day 5 and 6.**

A) *Pharmacokinetics*

Each subject will be his/her own control and each subject will sign an institutional review board–approved consent form explaining the purpose, nature, risks, benefits, and duration of the study. The study will be conducted in accordance with good clinical practice guidelines and with the ethical principles originating in the Declaration of Helsinki.

The subject's skin in the area of application (upper arm) will be relatively free of hair before gel or cream application. Blood samples (approximately 5 mL (1 tsp) each) will be drawn in BD vacutainer tubes. On Procedure Day 1, 2, 3, 4, 5 and 6, blood samples will be obtained as follows:

- Within 60 min pre-gel/cream application and then during wear, up to 25 h.

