2.2 Rationale

The goal of this study is to help establish more efficient pathways for approval of topical drug products by developing better tools to assess bioavailability. This study with a RLD and generic metronidazole topical gel, 0.75% and generic metronidazole topical cream, 0.75% will provide sufficient systemic concentrations of metronidazole to characterize the systemic bioavailability. The same products will also be studied (under a parallel but separate in vitro study protocol) using an in vitro permeation test (IVPT) model with excised human skin. The IVPT model has demonstrated IVIVC in previous studies using different drug molecules and formulations. This research will help establish whether the IVPT model correlates with and is predictive of in vivo bioavailability, and whether IVPT can be utilized as part of a collective weight-of-evidence approach to support an approval pathway for topical drug products.

These coordinated evaluations also collectively provide the in vivo reference datasets that are needed to establish IVIVC for the IVPT model which may then be utilized to support a new pathway for approval of numerous topical drug products for patients.

Metronidazole topical products

	Metronidazole gel, 0.75% (RLD) NDC: 66993-962-45	Metronidazole gel, 0.75% (generic) NDC: 0115-1474-46	Metronidazole cream, 0.75% (generic) NDC: 0168-0323-46
Inactive ingredients	0.8 mg of methylparaben and 0.2 mg of propylparaben as preservatives in a gel consisting of carbomer 940, edetate disodium, propylene glycol, purified water and sodium hydroxide	Carbopol 980, edetate disodium, methylparaben, propylene glycol, propylparaben, purified water and sodium hydroxide	Emulsifying wax, sorbitol solution, glycerin, isopropyl palmitate, benzyl alcohol, lactic acid, sodium hydroxide and purified water
Formulation	topical gel	topical gel	topical cream
Manufacturer	Prasco Laboratories	Impax Generics	Fougera Laboratories

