4 STUDY ENROLLMENT AND WITHDRAWAL

4.1 Subject Inclusion Criteria

Subjects are eligible for this study if they fulfill the inclusion criteria specified below:

1. Men or non-pregnant, women who are of any ethnic background between the age of 18 and 45 years old.
2. Subjects must be non-smokers/tobacco users (must have refrained from the use of nicotine-containing substances (e.g., cigarettes, cigars, chewing tobacco, snuff, gum, patches or electronic cigarettes) over the previous 2 months and are not currently smoking/using tobacco products.
3. Provide written informed consent before initiation of any of the study procedures.
4. Agree not to participate in another clinical trial/study during the study period or to participate in an investigational drug study for at least 1 month after the last study session.
5. Able to adhere to the study protocol schedule and study restrictions.
6. Able to participate in all study sessions.
7. Subjects have upper arms large enough to allow for the placement of 200 cm² [31 in²] area for application of gels or cream.
8. Subjects deemed to be healthy as judged by the Medically Accountable Investigator (MAI) and determined by medical history, physical examination and medication history.
9. Negative urine drug screening test (cannabinoids, amphetamines, barbiturates, benzodiazepine, cocaine, methadone, opiates, PCP).
10. Have normal screening laboratories for WBC, Hgb, platelets, sodium, potassium, chloride, bicarbonate, BUN, creatinine, ALT and AST.
11. Have normal screening laboratories for urine protein and urine glucose.
12. Female subjects must be of non-childbearing potential (as defined as surgically sterile [i.e. history of hysterectomy or tubal ligation] or postmenopausal for more than 1 year), or if of childbearing potential must be non-pregnant at the time of enrollment and on the morning of each procedure day, and must agree to use reliable hormonal or barrier birth control such as implants, injectables, combined

-
- oral contraceptives, some intrauterine devices (IUDs), sexual abstinence, or a vasectomized partner.
13. Agrees not to donate blood to a blood bank throughout participation in the study and at least 3 months after the last study session.

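### Section 5.2 gives the default t-test or ANOVA no pairing or subject effect, although every subject is to receive all three products; the within-subject model should be written down

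*Combined protocol and SAP*

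**What the plan says.** The Protocol Summary sets out a within-subject design: "The study will be an open-label, crossover study over 10 weeks (n=12 healthy subjects"). Under its Pharmacokinetics heading it adds: "Each subject will be his/her own control". Section 4.1 makes attendance at every session a condition of entry: "Able to participate in all study sessions". The schematic in Section 1 assigns the reference gel, the generic gel and the cream to sessions 1, 2 and 3.

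Section 5.2 then names the default test as Student's t-test or "Analysis of variance (ANOVA) followed by post-hoc Bonferroni test will be used, where appropriate". Its purpose is "comparing the differences in the means of the PK parameters and significant differences will be declared at" p below 0.05. No pairing, subject effect, repeated-measures term or list of product contrasts is given. Section 5.1 covers only how the PK parameters are estimated.

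Correlation within a person appears once, in the last-resort branch: "If no transformation can achieve normality, then will use permutation tests to compute empirical" p-values, and "will use the bootstrap to compute standard errors and confidence intervals that account for within-person correlation". The plan does not say whether the permutation is done within subject.

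Section 3.1 says the PK data will be used to judge whether the products are bioequivalent or not. Sections 2.1 and 2.2 give the cream's role as the inequivalent control and its composition.

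**The concern.** The fallback recognises the crossover structure and the default does not. An analyst could follow Section 5.2 to the letter with either an independent-samples test or a within-subject one, and the two can give materially different answers from the same 36 values of each parameter.

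Two readings of the results are exposed. A real difference between the cream and a gel could be missed, which would weaken the cream as the discriminating control. A non-significant gel-versus-gel result would also be easier to obtain. That result could then be taken as support for equivalence, because the only decision rule in Section 5.2 is a test of difference.

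**Working it through.** The plan states no power, variance, correlation or effect size, so it has no figure of its own to reproduce.

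**Inputs from the documents:** n = 12; three products; p < 0.05 with Bonferroni, hence 0.05/3 = 0.0167 per comparison if all three pairs are tested.

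**Assumed:** two-sided tests, complete data, normality on the log scale, a common within-subject correlation rho, and the CVs and cream/gel ratio below.

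**Step 1. Standard error.** With equal SD s, the true standard error of a difference between two product means is s × sqrt(2(1-rho)/12). An analysis with no subject term estimates s × sqrt(2/12). The ratio is 1/sqrt(1-rho):
- rho 0.3: 1/sqrt(0.7) = 1.20
- rho 0.5: 1/sqrt(0.5) = 1.41
- rho 0.7: 1/sqrt(0.3) = 1.83

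**Step 2. Size with equal SDs.** Simulated rejection rate per comparison at nominal 0.0167, for rho 0.1/0.3/0.5/0.7:
- one-way ANOVA: 0.012/0.005/0.0016/0.0002
- paired t-test: 0.016 to 0.017 throughout

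**Step 3. Power.** Assumed true cream/gel ratio 0.70, level 0.05/3, equal variances, log-scale variance ln(1+CV²), 100,000 replicates:

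| Within/between CV | rho | One-way ANOVA | Subject + product ANOVA | Paired t |
|---|---|---|---|---|
| 25%/40% | 0.71 | 21% | 82% | 75% |
| 30%/30% | 0.50 | 31% | 65% | 58% |
| 40%/40% | 0.50 | 13% | 39% | 34% |
| 40%/30% | 0.37 | 21% | 39% | 34% |
| 50%/30% | 0.28 | 15% | 25% | 22% |
| 40%/0% | 0 | 41% | 39% | 34% |

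Against one-way ANOVA, the subject + product ANOVA ranges from a gain of 61 points (82-21) to a loss of 2 (39-41). The paired t-test ranges from a gain of 54 (75-21) to a loss of 7 (34-41).

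**Step 4. Interval width.** Take 30%/30% CV and a true ratio of 1. The within-subject variance is ln(1.09) = 0.0862, and the total is twice that, 0.1724. The 90% limits are exp(±t × sqrt(2 × variance/12)):
- one-way, 33 df: 1.692 × 0.1695 = 0.287, giving 0.75 to 1.33
- paired, 11 df: 1.796 × 0.1199 = 0.215, giving 0.81 to 1.24

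**Step 5. Cost in degrees of freedom.** ANOVA goes from 36-3 = 33 to 33-11 = 22. A t-test goes from 24-2 = 22 to 12-1 = 11. The subject term widens the interval only if rho is below 1-(t without subject/t with subject)²:
- 95%, ANOVA: 1-(2.0345/2.0739)² = 0.04
- 95%, t-test: 1-(2.0739/2.2010)² = 0.11
- level 0.05/3, ANOVA: 1-(2.5222/2.5912)² = 0.05
- level 0.05/3, t-test: 1-(2.5912/2.8200)² = 0.16

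**Step 6. Unequal SDs.** In a subject + product ANOVA with one pooled error and assumed SDs 1, 1, 2 (odd product noisier), at rho 0.1/0.3/0.5:
- the odd product against another rejects 0.033/0.034/0.036 of the time
- the two like products reject about 0.001 to 0.002 of the time
- the familywise rate is 0.052/0.053/0.054

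With SDs 2, 2, 1 and rho 0.1, the familywise rate is 0.047. Pooling moves error between pairs but leaves the total near 0.05.

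**Step 7. Single order.** Take equal products, 30%/30% CV and an assumed drift of 0.1 log units per session in the order shown. The paired reference-gel-versus-cream test rejects about 17% of the time and one-way ANOVA 5%, against a nominal 1.7%.

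**The case against.** The strongest reply is that the unpaired reading is the least natural one. The protocol calls the study a crossover and treats each subject as the control. Section 5.2 qualifies its tests by appropriateness, and its fallback respects within-person correlation. A paired t-test is a Student's t-test, and a repeated-measures ANOVA is an ANOVA. This stands as far as it goes: a reader might infer from the silence that an independent-samples test was planned, and the documents do not support that inference. But compatibility is not specification, and the choice of error term should not be left until the data are in hand.

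A reader might go further and infer that a pooled-error ANOVA is too liberal, so that each contrast must carry its own paired error. That is not supported either. The ingredient list for the cream ("Emulsifying wax, sorbitol solution, glycerin, isopropyl palmitate, benzyl alcohol, lactic acid, sodium hydroxide and purified water") shows a different base from the gels, but it is not evidence of a different variance. Even at an assumed 2:1 SD ratio, the pooled subject ANOVA keeps familywise error, which is what Bonferroni is meant to control, at no more than about 0.055. Contrast-specific errors cost roughly 3 to 7 points of power when variances are equal.

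A third inference, that pairing guarantees the nominal level or adequate power, also fails. Step 7 shows that within-subject tests are more sensitive to period drift under a single order, and Step 3 shows that power can stay low.

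Finally, all the sizes rest on assumed CVs, correlations and ratios. That is correct, and it limits the magnitude. It does not remove the omission.

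**Conclusion.** The concern holds as under-specification. Section 5.2 does not tie its default tests to the crossover, and nothing elsewhere in the documents does so. If the tests are run without a subject term, variances are similar and rho is positive, the standard error is inflated by 1/sqrt(1-rho) and the test is conservative. At an assumed 30%/30% CV and a ratio of 0.70, power is about 31% without a subject term and 65% with one in the ANOVA. The advantage shrinks as rho falls and reverses slightly near zero. That the omission exists is certain from the text. How much it matters depends on variances and correlations that the documents do not give.

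**What to change.** In Section 5.2:
- State that the default model for Cmax and AUC includes product and subject effects, as a subject-plus-product ANOVA or as paired t-tests, and say which.
- State that any permutation test permutes product labels within subject.
- For objective 1, report product ratios of Cmax and AUC from log values with within-subject 90% confidence intervals, so that a non-significant difference is not read as equivalence.
- Optionally, add contrast-specific paired errors as a sensitivity analysis in case the cream's variance differs from the gels'. They need not be primary.
- State the limit: if all subjects follow the single product order in the Protocol Summary and schematic, a subject term does not separate product from period, and any drift between sessions enters the product comparison.

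The cost is a few sentences and standard code, with no new data. Statistically it is 11 error degrees of freedom, a net loss only below the break-even correlations in Step 5.

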3 OBJECTIVES

3.1 Study Objectives

- 1) Generate human PK data by collecting data following the application of three metronidazole formulations: RLD and generic metronidazole gel, 0.75% and generic metronidazole cream, 0.75%. This data will be used to assess the bioequivalence of these products or lack thereof.
- 2) To develop in vitro/in vivo correlation (IVIVC) models for dermal products. PK data from this study as well as in vitro data collected elsewhere from IVPT studies will be used to develop IVIVC models which could provide a surrogate for conducting clinical endpoint studies (required to demonstrate bioequivalence of dermal products).

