3.2 Study Outcome Measures

For the PK study the main outcome measure is the maximum serum concentration (C_{max}), time of maximum serum concentration (T_{max}) of metronidazole and area under the curve (AUC) attained from RLD and generic metronidazole gel, 0.75% and generic metronidazole cream, 0.75%.

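### Section 5.2 plans only tests of difference for a bioequivalence objective, and its optional Bonferroni step makes a real product difference easier to miss

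*Combined protocol and SAP*

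**What the plan says.** The first objective in section 3.1 covers all three products and states the purpose of the PK comparison: "This data will be used to assess the bioequivalence of these products or lack thereof". The protocol summary describes the two gels as therapeutically equivalent and the cream as an inequivalent control.

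Section 5.2 gives the comparison method in one sentence: a Student's t-test, or "Analysis of variance (ANOVA) followed by post-hoc Bonferroni test will be used, where appropriate". It compares means of the PK parameters and declares a difference at p < 0.05. The Bonferroni step is attached to the ANOVA. The text does not say which test serves which comparison, whether the t-test is paired, or which family of tests Bonferroni covers.

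Section 5.2 names two parameters, Cmax and AUC. Section 3.2 adds Tmax as a main outcome measure and ranks none of the three. No equivalence margin appears anywhere in the document. Confidence intervals are mentioned only in the bootstrap fallback of section 5.2, for data that no transformation makes normal.

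**The concern.** A bioequivalence conclusion needs evidence that the ratio of two products lies inside a stated margin. A difference test asks only whether the ratio can be distinguished from 1. In a small study it will often fail to do so for products that differ materially. If a non-significant result is then taken as a match, imprecision counts in favour of equivalence.

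In most trials a stricter threshold guards against the hoped-for claim. Here it works the other way for the gels, because it makes no difference the easier result to reach. It also makes the cream control harder to separate from the RLD. Since the wording leaves the route open, the analyst could pick the threshold after seeing the p-value. The results are also meant to feed the IVIVC models in the second objective, so a mislabelled comparison would carry forward.

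**Working it through.** The plan gives no power, effect size, CV or margin, so it has no figure of its own to reproduce.

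**Inputs from the document:** n = 12, three products given to each subject, threshold p < 0.05, Cmax and AUC in section 5.2. **Assumed:** two-sided tests, log scale, within-subject CV of 20% to 40%, true ratio 0.80.

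**1. Chance of missing a true ratio of 0.80**

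- Log difference: |ln 0.80| = 0.223.
- Within-subject SD: s = √ln(1 + CV²). Standard error of a contrast: SE = s·√(2/12). Noncentrality = 0.223/SE.
- Pooled error df for a subject-plus-product model: (12 − 1)(3 − 1) = 22. Critical t is 2.074 at 0.05 and 2.591 at 0.05/3 = 0.0167.
- Miss rate = probability that a noncentral t with 22 df falls within ± the critical value.

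| CV | s | SE | Noncentrality | Miss at 0.05 | Miss at 0.0167 |
|---|---|---|---|---|---|
| 20% | 0.198 | 0.081 | 2.76 | 25% | 43% |
| 30% | 0.294 | 0.120 | 1.86 | 57% | 74% |
| 40% | 0.385 | 0.157 | 1.42 | 73% | 86% |

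The last two columns differ by the chance that p falls between 0.0167 and 0.05: about 18 points at CV 20% and 17 points at CV 30%. In that band the same data give opposite reports depending on whether the correction is applied.

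A paired t-test has 11 df, and its miss rates are 29% at CV 20% and 60% at CV 30% with no correction. Comparing the two routes as they would probably be run (paired t at 0.05 with 11 df, pooled ANOVA contrast at 0.0167 with 22 df) gives 29% against 43%, and 60% against 74%. That is a gap of about 14 points.

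**2. False differences**

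Three pairs on two parameters make six tests.

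- *All three products equal, no correction.* If the tests were independent: 1 − 0.95⁶ = 26.5%. Simulated with 12 subjects, so that the pairs share data: 23.2% when the parameters are uncorrelated and 19.6% at correlation 0.8.
- *Cream truly different, gels equal.* Only gel versus gel is a true null, so there are two null tests: 1 − 0.95² = 9.8% if independent, about 8% at correlation 0.8. With Bonferroni over the three pairs: 1 − (1 − 0.0167)² = 3.3%, and about 3% with correlation.

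**The case against.** Several points on the other side are sound.

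- *Section 5.2 does not say that non-significance will be read as equivalence.* True: it says only when a difference is declared. But it supplies no other route to the bioequivalence conclusion that section 3.1 calls for, so the gap stands.
- *An ordinary reading of the sentence is a t-test for two products and ANOVA with Bonferroni for three.* That is plausible, and a reader who infers that three uncorrected t-tests are planned is reading it from silence. However, generic gel versus RLD is itself a two-product comparison inside a three-product study, so the ambiguity falls on the comparison that matters most.
- *Bonferroni is not the cause.* Correct. At CV 30% the miss rate is already 57% without it. The correction aggravates a problem that comes from testing for difference with 12 subjects.
- *The all-equal null contradicts the design.* Also correct. A reader might count nine tests by adding Tmax and conclude that both routes badly inflate false differences. Section 5.2 names two parameters; Tmax is a main outcome only in section 3.2. If the cream differs, as the protocol expects, the Bonferroni route stays near 3%.
- *Generic gel versus cream is a legitimate comparison.* It is. The first objective covers all three formulations, so the documents do not support calling it irrelevant.

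**Conclusion.** The concern holds as a mismatch between objective and analysis. Section 5.2 cannot deliver a bioequivalence conclusion, and its optional Bonferroni step makes a false finding of no difference more likely: 25% to 43% at CV 20%, and 57% to 74% at CV 30%, for a true ratio of 0.80. The open choice of test allows a p-value between 0.0167 and 0.05 to be reported in either direction.

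False differences are secondary: about 20% to 23% for uncorrected tests of all pairs if every product is equal, but 8% to 10% if only the gels are equal, and about 3% with Bonferroni. The documents do not support the stronger statement that both stated routes give an inflated error rate.

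The directions do not depend on the assumptions; the sizes do. CV, true ratio and correlation between parameters are not in the documents, and a different CV moves the miss rates substantially.

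**What to change.** Replace the test sentence in section 5.2 with the following elements.

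1. One within-subject model on log Cmax and log AUC, with planned contrasts generic gel/RLD and cream/RLD. The schematic shows the same product order in every session and describes no alternative sequences. Under that order a period term cannot be separated from product, and the report should say so.
2. Each contrast as a geometric mean ratio with an unadjusted 90% CI, judged against an equivalence margin stated in advance. The sponsor must supply the margin.
3. Gel equivalence claimed only if both parameters lie within the margin. Because both must pass, that joint claim needs no alpha adjustment.
4. A separate rule for the cream, since failing an equivalence test does not show inequivalence. For example: inequivalent only if the CI lies wholly outside the margin on one named parameter, otherwise inconclusive.
5. Tmax and generic gel versus cream reported as supportive estimates, which also reconciles sections 3.2 and 5.2.

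The t-test option and the Bonferroni step then go.

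The cost is wording only, with no added subjects, samples or assays. Generic gel versus cream becomes descriptive, and some comparisons may end as inconclusive. As an illustration with an assumed margin of 0.80 to 1.25, truly equal products and 11 df, one parameter would pass about 65% of the time at CV 20% and 16% at CV 30%. That is a limit of 12 subjects which the present wording hides.

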2 BACKGROUND INFORMATION AND SCIENTIFIC RATIONALE

2.1 Background Information

Generic drugs are approved based upon bioequivalence (BE) testing, and with respect to oral drug delivery, the accepted BE approach is relatively straightforward and is principally based on matching blood level profiles. In some cases, in vitro dissolution tests can be done to help determine the bioequivalence of an oral dosage form. For topical drug products in the United States, with the exception of corticosteroids and a few other products, a comparative clinical endpoint study is often necessary for approval of a generic product or for replacement of an approved dermatological drug product with one that has major changes. Comparative clinical trials are relatively insensitive, time-consuming and costly. It is especially difficult to gain the adequate statistical power needed to evaluate bioequivalence for some dermatological conditions, and can require a large number (i.e., hundreds^{1,2}) of subjects.

This study supports FDA's continuing effort to identify the most accurate, sensitive, reproducible and efficient methods to evaluate topical dermatological drug products.

The model drug for this study is metronidazole, which is available in different topical formulations, gel, cream and lotion, approved by the United States FDA. The metronidazole gels and cream have been chosen for this study because the therapeutically equivalent metronidazole gels will be used to evaluate BE in vivo. The metronidazole cream is being used as the non-BE control for this project.

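### Objective 1 asks for a bioequivalence assessment, but section 5.2 plans only tests of difference at p < 0.05 and gives no equivalence criterion

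*Combined protocol and SAP*

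**What the plan says.** Section 3.1 states for Objective 1: "This data will be used to assess the bioequivalence of these products or lack thereof". Section 2.1 gives each product a role. It says that "the therapeutically equivalent metronidazole gels will be used to evaluate BE in vivo", and for the third product: "The metronidazole cream is being used as the non-BE control for this project".

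Section 5.2 describes the aim more narrowly, as determining Cmax and AUC. Its comparative analysis is a t-test, or ANOVA followed by Bonferroni, which "will be used, where appropriate, for comparing the differences in the means of the PK parameters and significant differences will be declared at" a threshold of 0.05. It does not say whether the t-test is paired.

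If the data are not normal, Box-Cox transformations are tried. If none works, permutation tests supply p-values and the plan "will use the bootstrap to compute standard errors and confidence intervals that account for within-person correlation". No confidence level is given for those intervals, and no limits to compare them with.

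**The concern.** A test of difference takes equality as its null hypothesis. Rejecting it supports a difference. Failing to reject it may reflect equal products, noisy data or too few subjects, and the test cannot tell these apart. An equivalence claim needs the reverse: a stated margin, and evidence that the true ratio lies inside it.

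At stake is the equivalence half of Objective 1. Followed literally, the plan gives no verdict on the two gels and no definition of the cream having behaved as a non-equivalent control. The likely informal substitute, reading non-significance as equivalence, rewards noisy data. Bonferroni makes that worse for the gel comparison because non-significance becomes easier to reach. For detecting a difference with the cream, Bonferroni is merely conservative.

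**Working it through.** **Plan's own figures.** There is none to reproduce: the documents give no margin, CV, expected ratio, power or justification of the sample size.

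**Is a criterion given anywhere?**
- Sections 2.1 and 3.1 state the bioequivalence purpose but no rule.
- Section 3.2 names Cmax, Tmax and AUC as outcomes but no rule.
- Section 5.1 describes non-compartmental estimation only.
- Section 5.2 gives tests of difference. Its permutation fallback is also a test of difference, and its bootstrap intervals have no limits.

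The omission is therefore complete, and the main conclusion needs no arithmetic. The arithmetic below sizes the consequence if non-significance were taken as equivalence.

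**Inputs**
- From the Protocol Summary: crossover, n = 12.
- From section 5.2: alpha 0.05, taken as two-sided.
- Assumed: 0.05/3 for Bonferroni over three pairwise comparisons; within-subject CV 10% to 30%; limits 0.80 to 1.25; paired log-scale analysis; no period or carry-over effect.

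**Formulas**
- Within-subject SD on the log scale: s = sqrt(ln(1 + CV²)).
- Standard error of the log ratio: SE = s × sqrt(2/12), with 11 degrees of freedom.
- Noncentrality: ln(true ratio)/SE. The probability of non-significance is that a noncentral t falls between minus and plus the critical value, which is 2.201 at 0.05 and 2.820 at 0.05/3.
- Two one-sided tests (TOST): pass if the 90% interval lies wholly within 0.80 to 1.25 (t = 1.796).

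**Worked case, CV 20%, true ratio 0.80.** s = sqrt(ln 1.04) = 0.198; SE = 0.198 × 0.408 = 0.081; noncentrality = -0.223/0.081 = -2.76. The probability of non-significance is 29% at 0.05 and 50% at 0.05/3.

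**Per parameter, true ratio 0.80**

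| CV | Non-significant at 0.05 | Non-significant at 0.05/3 |
|---|---|---|
| 10% | 0.1% | 1% |
| 15% | 9% | 22% |
| 20% | 29% | 50% |
| 30% | 60% | 78% |

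TOST passes such a product at most about 5% of the time. At true ratio 0.70, the non-significance rates are 2% and 8% at CV 20%, and 23% and 42% at CV 30%.

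**Both Cmax and AUC required to be non-significant** (ratio 0.80 for both, correlation 0 to 0.9)

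| CV | At 0.05 | At 0.05/3 |
|---|---|---|
| 15% | 1-6% | 5-16% |
| 20% | 8-22% | 25-42% |
| 30% | 36-53% | 61-72% |

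**Evidence in a non-significant result.** At ratio 1.0 it occurs 95% of the time at 0.05. Against ratio 0.80 it therefore favours equality by 95/9, about 11 to 1 (unrounded), at CV 15%; by 95/29 = 3.3 to 1 at CV 20%; and by only 95/60 = 1.6 to 1 at CV 30%.

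**Opposite direction.** At ratio 0.90 and CV 10%, 65% of trials are significant at 0.05 (44% at 0.05/3), although 86% pass TOST.

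**Sensitivity to pairing and scale.** Section 5.2 does not say paired and reaches the log scale only after non-normality. On the untransformed scale, with ratio 0.80, CV 20% and an assumed between-subject CV of 30%, non-significance occurs 33% and 56% of the time if paired, and 78% and 92% if unpaired. The paired log figures are not the unfavourable case.

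**The case against.** The strongest defence is that this is an estimation study. Section 5.2 frames its aim as determining PK parameters, the Protocol Summary already calls the gels therapeutically equivalent and the cream an inequivalent control, the data feed the IVIVC work, and no approval decision is said to rest on the test. That limits the consequence. It does not supply the criterion that the bioequivalence purpose in sections 2.1 and 3.1 needs.

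Second, no section says that non-significance means equivalence, so the false-pass rates describe a reading the plan does not adopt. This stands: the defect shown is the absence of a verdict rule, and the rates show what the obvious substitute would cost. Likewise, significance at ratio 0.90 is a correct result for a test of difference; it misleads only if read as inequivalence.

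Third, the size depends on assumed CVs and limits. At CV 10% non-significance would rarely mislead at ratio 0.80, and the documents do not say where this study lies in the range.

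Fourth, the Protocol Summary and the study schematic give the same product order in every subject, and no randomised order is stated. Any period effect is therefore part of each product contrast. This applies equally to the planned tests and to the replacement below, and it belongs in the plan as a caveat.

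**Conclusion.** The concern holds, and section 5.2 is wrong as written for the equivalence half of Objective 1. The stated method cannot support equivalence, and neither the main analysis nor the fallback supplies a criterion. This conclusion rests on the text alone.

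The practical size is conditional. With 12 subjects, limits of 80-125% and CV 20% to 30%, treating non-significance as equivalence would pass a product at ratio 0.80 about 29% to 60% of the time per parameter at 0.05, against at most about 5% with TOST. At CV 10% the corresponding figure is 0.1%. All these rates assume no period or carry-over effect.

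**What to change.** In section 5.2:
- Make the bioequivalence analysis the within-subject geometric mean ratio, on the log scale, of Cmax and of AUC over 0-25 h, each with a 90% confidence interval. Generic gel over RLD gel is primary; cream over RLD gel is the negative control.
- Declare bioequivalence only if the interval lies wholly within pre-stated limits (for example 80.00-125.00%) for both parameters, without Bonferroni. Otherwise report that bioequivalence was not shown, and call the result inconclusive if the interval crosses a limit.
- For the cream, state that the control behaves as expected if it fails this criterion. Report separately whether its interval lies wholly outside the limits, which is stronger evidence.
- Keep the difference tests as descriptive support, and say how Tmax, a main outcome in section 3.2 that section 5.2 does not name, will be reported.
- State the CV assumed for 12 subjects and the resulting chance of an inconclusive result.
- Add that the interval and its 5% error rate assume no period or carry-over effect, which the fixed product order cannot separate from product.

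**Cost.** No new data, but an honest statement about precision. With 12 subjects and limits of 80-125%, at true ratio 1.0:

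| CV | TOST power, one parameter | Both parameters (correlation 0.8) | Subjects for 80% power, one parameter |
|---|---|---|---|
| 15% | 92% | 88% | 10 |
| 20% | 65% | 52% | 15 |
| 25% | 35% | 21% | 23 |
| 30% | 16% | 6% | 32 (31 falls just short) |

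The cream control is also limited. At ratio 0.70 its interval lies wholly outside the limits only about 46% (CV 20%) or 28% (CV 30%) of the time per parameter. The difference test is then significant 98% and 77% of the time at 0.05 (92% and 58% at 0.05/3), which is a reason to keep it as support. Failing the criterion is weak evidence alone: a product with true ratio 1.0 fails it 100 - 65 = 35% of the time at CV 20% and 100 - 16 = 84% at CV 30%.
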